Normal volunteers will be enrolled on this 3-5 week study that includes 3 visits to the NIH Clinical Center. Subjects may be contacted by telephone, text or email to verify study compound compliance, for AE/safety assessment and to remind subjects to initiate the 24-hour fast prior to Visit #2 and Visit #3. Email communications will be made through the NIH medical secure email system unless the patient declines its' use and requests standard unsecure email. A schematic showing the outline of the overall study is shown below.

The variable length of the washout and study arms phase is to allow flexibility for the scheduling of subject visits. The prior pharmacokinetic studies support that 7 days is more than sufficient to restore NAD⁺ levels to baseline.

The following actions will be undertaken at the defined visits:

Arm 1

Screening/Visit 1:

- Subjects will be screened for inclusion or exclusion.
- Baseline screening laboratories performed.
- Pregnancy testing in women of childbearing potential.

- Eligible subjects will be randomized to placebo (i.e. sugar tablet) or 1 gram of NR daily. The study compound start date will be determined at this visit. Start date will be within one week of screening visit.
- Instruct subject on study compound administration, reinforce maintenance of stable diet and activity level during the study participation period, and review the time of the breakfast on day 6 (+3 days, if needed), prior to initiating the 24-hour fast.

Day 1 of Arm 1 study compound administration.

A member of the research team may contact study subjects:

- to remind them which day to initiate therapy
- to remind subjects of the 24-hour \pm 2hr fast

Visit 2: Day 7 (+ up to 3 days, if needed) of Arm 1 study compound administration

- Subjects will arrive at the Clinical Center after a 24-hour fast ± 2 hours with the
 exception of drinking water starting the morning of day 6 (+ up to 3 days, if
 needed).
- A pill count will be performed to evaluate compliance.
- Fasting blood draw for hepatic panel, acute care panel, insulin, growth hormone, complete blood count, serum immune cell studies and to measure NAD levels.
- Urine collection for ketones
- Administer day 7 (+ up to 3 days, if needed) Arm 1 placebo/NR capsules.
- A 500 caloric meal will be eaten.
- Refed blood-draw for insulin, growth hormone, glucose, serum immune cell studies and to measure NAD levels three hours ± 30 minutes after fixed caloric meal (metabolic kitchen).

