The pharmacist Co-Investigator on the study will devise a randomization code in consultation with [name] (Biostatistician). This code will be kept confidential and will be employed by the pharmacy to dispense the study pills. For each arm, subjects would receive sufficient pills for 7 days of administration. If additional pills are needed to extend the treatment arm by up to three days, these will be dispensed separately by the pharmacy. Subjects will take their study medication at home for days 1 through 6 (+ up to 3 days, if needed). Day 7 (+ up to 3 days, if needed) dosing will be in the clinic. Subjects will be instructed to bring their study medication bottle back to the clinical center for day 7 (+ up to 3 days, if needed) dosing and to not take the day 7 (+ up to 3 days, if needed) dose until instructed to by the study team. If the subject forgets to bring the study bottle with the day 7 (+ up to 3 days, if needed) dose, the day 7 (+ up to 3 days, if needed) dose will be ordered through CRIS from the pharmacy. A process has been developed by the NHLBI pharmacist to ensure the subject receives the correct study compound or placebo. The day 7 (+ up to 3 days, if needed) pill for each arm will be given to the study subject for consumption following the 24-hour fasting research blood draw. The study pill receptacle will have the subject's name, code number, prescription details (4 tablets by mouth each morning with or without food) and will include the arm (1 or 2). If the study subject does not bring in the pill bottle, the subject will be asked to confirm the number of study doses taken over the prior 6 (+ up

Amendment F, May 22, 2018 [name], PhD to 3 days, if needed) days and this will be documented in the medical record. The pill bottles will then either be collected at the next visit or we will have the subject return by FedEx. The code will be shared with the statistician following the completion of studies on 20 subjects to evaluate observed standard deviations to assess original study assumptions and continued study feasibility.

Description of Study Population and Recruitment

Participants will be enrolled at the NIH Clinical Center. Subjects will be recruited through a LISTSERV email announcement and study procedures will be performed in the outpatient unit/day hospital at the NIH Clinical Center. A list of healthy volunteers may also be requested from the NIH Office of Patient Recruitment.

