All tests will follow NIH Clinical Center policies. Any of the listed procedures or laboratory tests performed within three months prior to enrollment in this protocol may/may not be repeated. However, if these procedures are not repeated, the prior studies (within the last 3 months) will be reviewed in CRIS as part of the protocol. The purpose for not repeating study procedures is to prevent unnecessary inconveniences, risks or discomforts for study participants and the NIH Clinical Center.

- *i)* **Blood Draws:** In addition to the screening blood draw (40 mL), subjects will have 4 additional research blood draws up to 100 mL each, as described in Section 4.
- *ii) Urine Analysis:* Subjects will be asked to provide up to three urine samples, one for pregnancy testing as part of screening evaluation and two in the fasting state at Visits 2 and 3 as described in Section 4.
- *iii)* 24-Hour Fasting: Subjects will be asked to fast for up to 26 hours (water intake will not be restricted) during each of the two treatment arms.
- *iv) Fixed Caloric Meal:* The meal will be a 500 calorie breakfast. Subjects will have a choice of two meals.

| Meal Choices | Description of Meal | | | | |
|--------------|---|--|--|--|--|
| Option 1 | Vegetable omelet | | | | |
| | Toast with butter and jelly | | | | |
| | Orange juice | | | | |
| Option 2 - | Oatmeal with Walnuts, Brown Sugar and Dried | | | | |
| | Cranberries | | | | |
| | • Milk | | | | |

8. Dietary Supplement

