- Flow cytometry to explore innate and adaptive cell profiles (assessment of cell surface markers to assay cellular polarity and activation)
- Negative selection to extract T-cells to investigate primary culture T-cell polarity (ELISA assays to measure cytokine production following T-cell activation)
- Serum samples for SomaLogic Proteome analysis and Luminex analysis of cytokine levels (discovery proteomics data collection)
- ELISPOT analysis of T_H1/T_H2/T_H17 cytokine polarity following TCR crosslinking (Alternate assay to measure CD4 T-cell polarity)

In this pilot study, the parametric paired Student t-test and the non-parametric Wilcoxon Signed Rank test will be used to analyze treatment differences in secondary outcome measurements.

11. Stopping Rules for Subjects

- Pregnancy and breastfeeding
- Subjects taking less than 75% of the supplement
- Any other significant medical symptoms that may or not be related to the treatment and as determined by contact with the physician
- Subjects who are found to be pregnant or wish to breastfeed during the study will automatically be withdrawn. A pregnancy screening will be done for all female volunteers at the first visit and subjects will be excluded from the study if pregnant

12. Data and Safety Monitoring

Safety Monitoring

Accrual and safety data will be monitored by the Principal Investigator, [name]. Ph.D., who will provide oversight to the conduct of this study.

Accrual and safety data will be monitored and reviewed annually by the Institutional Review Board (IRB). Prior to implementation of this study, the protocol and the proposed subject informed consent document will be reviewed and approved by the properly constituted IRB operating according to the 45 CFR 46. This committee must approve all amendments to the protocol or informed consent document, and conduct continuing annual review so long as the protocol is open to accrual or follow up of subjects.

Adverse Event Reporting

Adverse Event (AE): Any untoward medical occurrence in a human subject, including any abnormal sign (e.g., abnormal physical exam or laboratory finding), symptom, or disease, temporally associated with the subject's participation in the research, whether or not considered related to the subject's participation in the research.

Abnormal laboratory values: A moderate and severe abnormal laboratory value will be considered an AE if the laboratory abnormality is characterized by any of the following:

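### Minor, inexpensive safety improvement: repeat the pregnancy test at Visit 2, because women given placebo first start NR about 13 to 31 days after the only scheduled test

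*Combined protocol and SAP*

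**What the plan says.** Section 11 (Stopping Rules for Subjects) states: "A pregnancy screening will be done for all female volunteers at the first visit and subjects will be excluded from the study if pregnant". Section 5 puts the same check in the Screening/Visit 1 list: "Pregnancy testing in women of childbearing potential". Section 7 ii allocates the urine samples: "one for pregnancy testing as part of screening evaluation and two in the fasting state at Visits 2 and 3". In Section 5 the Visit 2 and Visit 3 urine is for ketones, and neither visit list contains a pregnancy test.

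On timing, Section 5 says of Arm 1: "Start date will be within one week of screening visit". Visit 2 falls on Arm 1 Day 7, extendable by up to three days. Arm 2 bottles are handed out at Visit 2, a washout of 7 to 14 days follows, and Arm 2 dosing begins at home. There is no clinic visit between Visit 2 and the first Arm 2 dose.

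The protocol has these safeguards:
- Reliable contraception is an entry condition (Section 6) and is required while enrolled (Section 13). Its use is checked at telephone screening and at the screening visit.
- A woman found to be pregnant is withdrawn automatically (Section 11). The pregnancy is reported as an unanticipated problem and followed to its conclusion (Section 12).
- βHCG is among the laboratory tests that may be done (Section 6).
- Study staff ask about adverse events (Section 12). Contact between visits is optional: "Subjects may be contacted by telephone, text or email to verify study compound compliance, for AE/safety assessment".

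**The concern.** Section 13 excludes pregnant women because NR is not known to be safe for them. In a crossover, the test that supports this exclusion has to serve two dosing periods. For NR-first women it is at most a week old at first exposure. For placebo-first women, about half if the sequences are balanced, first exposure comes only in Arm 2, after Arm 1 and the washout. Nothing scheduled in between would detect an early, unrecognised pregnancy, although urine is collected on the day the Arm 2 supply is released.

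What is at stake is avoidable fetal exposure to NR in a study with no direct benefit to participants. The sample size and primary comparison are not at stake, except for the rare loss of one subject's pair.

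**Working it through.** **Inputs from Section 5.** Visit 1 is day 0. Arm 1 Day 1 is day 0 to 7. Visit 2 is 6 to 9 days after Arm 1 Day 1. Washout is 7 to 14 days. Visit 3 is 6 to 9 days after Arm 2 Day 1.

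**Check against the stated study length (3-5 weeks).** Arm 1 Day 1 to Visit 3, counted inclusively, is 20 to 33 days, or 21 to 34 if the washout is counted as full days in between. That is 2.9 to 4.9 weeks, so the timeline reproduces the stated length when counted from the first dose.

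**Interval from Visit 1 test to first NR, placebo-first women.**
- Visit 2: 0 + 6 = day 6 to 7 + 9 = day 16.
- Arm 2 Day 1: 6 + 7 = day 13 to 16 + 14 = day 30. With the full-day count, day 14 to 31.
- The upper ends need every window at its maximum. If five weeks were a limit from Visit 1 to Visit 3, the latest Arm 2 Day 1 would be 35 - 6 = day 29.

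**With a test at Visit 2.** The interval from last test to first NR becomes the washout alone: 7-14 (or 8-15) days.

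**Share of the gap covered, in calendar days.**
- All windows short: 6/13 = 46% (6/14 = 43%).
- All windows long: 16/30 = 53% (16/31 = 52%).
- Mixed extremes: 6/21 = 29% to 16/23 = 70%.

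**Share of at-risk conceptions caught, allowing for detection lag.** Suppose a test misses conceptions in the preceding L days. The documents give no value; I take L = 7 and L = 14. The Visit 1 test then leaves L further days uncovered, while the Visit 2 test still gains only 6 to 16 days. The share is (Visit 2 day) / (Arm 2 Day 1 + L):

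| L | All windows short | All windows long |
|---|---|---|
| 7 | 6/20 = 30% (6/21 = 29%) | 16/37 = 43% (16/38 = 42%) |
| 14 | 6/27 = 22% (6/28 = 21%) | 16/44 = 36% (16/45 = 36%) |

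On these schedules more conceptions are missed than caught. Mixed schedules run from 6/(21 + 14) = 17% to 16/(23 + 7) = 53%, so a long Arm 1 with a short washout and L = 7 is an exception.

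**Expected numbers.** Assumptions not in the documents: half of subjects are women able to conceive, half of those are placebo-first, and conception on contraception is 0.5-1% per 30 days. Section 10 gives a ceiling of 42 and 20 enrolled by October 2017, so at most 22 remained. That is 11 women, 5.5 of them placebo-first. Fewer may remain at Amendment F (May 2018).
- Caught by a Visit 2 test: 5.5 × 0.005 × 6/30 = 0.006 to 5.5 × 0.01 × 16/30 = 0.03.
- Missed, L = 7: 5.5 × 0.005 × 14/30 = 0.013 to 5.5 × 0.01 × 22/30 = 0.040.
- Missed, L = 14: 5.5 × 0.005 × 21/30 = 0.019 to 5.5 × 0.01 × 29/30 = 0.053.
- Caught if a test on Arm 2 Day 1 is added: 5.5 × 0.005 × 13/30 = 0.012 to 5.5 × 0.01 × 31/30 = 0.057.

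**False positives.** Testing all 11 women would find 11 × 0.005 × 6/30 = 0.011 to 11 × 0.01 × 16/30 = 0.059 new pregnancies across both sequences. Dividing by 11 tests, false alarms outnumber true positives once the false-positive rate exceeds about 0.1% to 0.5% per test.

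**The case against.** The strongest reply is that the risk is already managed. Contraception is mandatory, women seeking pregnancy cannot take part, a test on suspicion is permitted, and any pregnancy leads to withdrawal and reporting. The consent form was not available for this review, so instructions there on suspected pregnancy cannot be judged. What remains is a routine test in women without symptoms, with an expected yield far below one. This stands as a reason to rate the point minor. It does not supply a scheduled retest: contraception use is checked only at entry, contact between visits is optional, and permission to test is not a schedule.

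A second reply is that Visit 2 is the wrong day, since it falls 7 to 15 days before first NR in the group it mainly helps, and for NR-first women it can spare only the one clinic dose. This stands in part. A home test on Arm 2 Day 1 covers more of the gap but depends on the subject to do it and act on it. The Visit 2 test is read by staff before any Arm 2 supply leaves the clinic.

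Third, at such low prevalence a positive may well be false. This also stands, and is why confirmation must come before withdrawal.

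A reader might infer more than the documents support:
- **That a Visit 2 test halves the risk.** Half is a share of calendar days; with a detection lag the share of conceptions caught is generally lower.
- **That the pregnancy test may be three months old.** Section 7 allows recent tests not to be repeated and does not exempt this one, but Sections 5 and 11 place pregnancy screening at the first visit.
- **That the protocol contradicts itself.** Sections 5, 7 and 11 agree on one test at Visit 1.

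**Conclusion.** The point holds as a minor, inexpensive improvement to participant safety. It is not an error in the plan and does not affect its statistics. The 13-30 (or 14-31) day interval follows from the protocol's own windows. A Visit 2 test would shorten it to 7-14 (or 8-15) days.

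The absolute benefit is very small and rests on assumed conception rates, sex mix and detection lag, as well as on how many subjects are still to pass Visit 2. The case for the change is that the urine is already being collected, not that the present risk is large.

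**What to change.** Amend Section 7 ii and the Visit 2 list in Section 5 so that the fasting urine is also tested for pregnancy in all women of childbearing potential. All must be tested because sequence is blinded.
- Read the result before the clinic dose ("Administer day 7 (+ up to 3 days, if needed) Arm 1 placebo/NR capsules") and before Arm 2 bottles are released. Section 5 already has the dose follow the fasting draw: it "will be given to the study subject for consumption following the 24-hour fasting research blood draw".
- If positive, hold both, confirm by βHCG (for example on blood from the fasting draw), and withdraw under Section 11 only once confirmed.
- Reconfirm and record contraception use at this visit.
- Optionally, dispense a home urine test for the morning of Arm 2 Day 1, with the instruction not to dose and to call the team if positive. Like any test, it would still miss the most recent conceptions.
- In the same amendment, state that the three-month allowance in Section 7 does not apply to the pregnancy test.

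**Cost.** An IRB-approved amendment, probably with a consent update, and one urine test per woman still to reach Visit 2 (at most about 11 on the assumptions above, twice that with the home test). No visit or sample is added. The dose and meal wait for the result. Section 7 iii allows some room ("Subjects will be asked to fast for up to 26 hours") and the refed draw is timed from the meal, so a prompt result should not disturb the schedule; the documents give no turnaround time. A positive result, true or false, may delay the visit or lose that subject's pair.
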